# Study Protocol

## Background and Rationale

Patients undergoing cataract surgery increasingly expect functional vision at distance, intermediate, and near without disturbing photic phenomena. Standard monofocal IOLs offer excellent distance acuity but limited intermediate and near vision. Enhanced monofocal and extended depth-of-focus (EDOF) lenses aim to broaden the range of clear vision while minimizing dysphotopsia. This study compares outcomes across these IOL categories.

## Objectives

**Primary Objective:** To compare binocular uncorrected distance, intermediate, and near visual acuity and patient satisfaction at 6 months among monofocal, enhanced monofocal, and EDOF IOLs.

**Secondary Objectives:** To compare monocular and binocular corrected acuities, refraction, defocus curve performance, and halo/glare symptoms among the three IOL groups.

## Study Design

Consecutive, comparative, retrospective case series of patients undergoing bilateral phacoemulsification with implantation of the same IOL model in both eyes.

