## Study Period

June 2019 to January 2024. Primary completion in 2024.

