## Exclusion Criteria

- Preoperative corneal astigmatism  $\geq 1.0$  D.
- Axial length  $\leq 21$  mm or  $\geq 26$  mm.
- Prior intraocular or corneal surgery.
- Ocular comorbidities affecting vision (severe dry eye, amblyopia, ocular surface disease, corneal pathology, retinal diseases, uveitis, glaucoma, pseudoexfoliation, pterygium).
- Intraoperative or postoperative complications, or failure to complete 6-month follow-up.

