## Interventions / Exposures

Patients received one of the following IOLs in both eyes:

- Monofocal: Tecnis ZCB00 (Johnson & Johnson Vision)
- Enhanced monofocal: Tecnis Eyhance ICB00 (Johnson & Johnson Vision)
- EDOF: Asqelio EDOF ETLIO130C (AST Products)

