### Primary Outcomes (6 months):

- Binocular UDVA, UIVA, UNVA (logMAR).
- Patient satisfaction scores for distance, intermediate, and near spectacle-free vision (0–10 scale).

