## **Comparative Analyses**

- Kruskal–Wallis tests with Dunn–Bonferroni post hoc comparisons for non-normally distributed continuous outcomes.
- One-way ANOVA with Tukey HSD for key binocular outcomes when appropriate.
- Chi-square or Fisher’s exact tests for categorical variables.
- GEE model with exchangeable correlation structure for binocular UIVA to account for within-subject correlation.

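### The primary three-lens comparison is non-randomised, and no planned analysis names a covariate, so confounding is limited only partly, by eligibility, and not by the analysis.

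*Combined protocol and SAP*

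**What the plan says.** The protocol's Study Design section calls the study a "Consecutive, comparative, retrospective case series of patients undergoing bilateral phacoemulsification with implantation of the same IOL model in both eyes". Interventions / Exposures adds only that "Patients received one of the following IOLs in both eyes", and gives neither an allocation rule nor the reason a patient had one lens and not another. The Study Period is "June 2019 to January 2024", with no statement that the three lenses were in use over the same dates.

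The primary objective is to compare three binocular uncorrected acuities and patient satisfaction "among monofocal, enhanced monofocal, and EDOF IOLs". Satisfaction is scored separately for three distances, so there are six primary outcomes.

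The SAP's Comparative Analyses section lists four methods:
- Kruskal–Wallis with Dunn–Bonferroni comparisons
- "One-way ANOVA with Tukey HSD for key binocular outcomes when appropriate"
- chi-square or Fisher's exact tests for categorical variables
- a GEE for binocular UIVA, whose stated purpose is within-subject correlation

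No covariate, stratification, matching, propensity method or sensitivity analysis is named anywhere in the document.

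**The concern.** Without randomisation, patients given different lenses may differ in ways that affect acuity or satisfaction. The first three methods, as written, have lens group as their only factor. The GEE could carry covariates, but it names none and covers one of the six primary outcomes. If the plan is followed as written, any imbalance in a prognostic factor passes into the lens contrast uncorrected. The main conclusion is comparative, so this bears on the central result. It also bears on the p-values, because a rejection could reflect who received each lens and not what the lens does.

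**Working it through.** **The plan's own figure.** Sample Size gives N = 197, three groups, f = 0.25, alpha 0.05 and power 0.96. With noncentrality λ = N f² = 197 × 0.0625 = 12.31 on 2 and 194 degrees of freedom, the noncentral F distribution gives power 0.887. The stated 0.96 is not reproduced. That is a separate matter, and the argument here does not depend on it.

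**What eligibility leaves open** (Study Population, Exclusion Criteria, Study Period):
- Age 45 to 75: a span of 30 years.
- Axial length above 21 and below 26 mm: a span of 5 mm.
- Corneal astigmatism: any value below 1.0 D.
- Study period June 2019 to January 2024: about 4 years 7 months. If the 6-month follow-up falls inside it, surgery still spans about 4 years 1 month.
- Preoperative acuity: no limit stated.

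**Illustration of size.** A covariate with correlation r to the outcome and standardised imbalance d between the extreme lens groups shifts that contrast by b = r × d outcome SD. The documents give neither r nor d, so these are assumptions shown over a range: 0.2 × 0.3 = 0.06, 0.3 × 0.5 = 0.15 and 0.4 × 0.8 = 0.32. Suppose there is no true lens effect and 197 patients are split equally. The split is also assumed, because group sizes are not given.

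- Equally spaced shifts (−b/2, 0, +b/2): f² = b²/6, so λ = 197 b²/6.
- One group shifted by b: f² = 2b²/9, so λ = 197 × 2b²/9.

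| b (SD) | λ, equally spaced | Rejection rate | λ, one group | Rejection rate |
|---|---|---|---|---|
| 0 | 0 | 5% | 0 | 5% |
| 0.06 | 0.118 | 5.9% | 0.158 | 6.2% |
| 0.15 | 0.739 | 10.9% | 0.985 | 13.0% |
| 0.32 | 3.362 | 35% | 4.483 | 45% |

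As a yardstick, f = 0.25 with equally spaced means is a range of 0.25 × √6 = 0.612 SD, so the three biases are about 10%, 24% and 52% of it. If one group differs, f = 0.25 is 0.25 × √(9/2) = 0.530 SD, and the shares are about 11%, 28% and 60%. The two patterns should not be mixed.

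**Cost of adjusting.** With c covariates, λ = N f² / [(1 − R²) × VIF] on 2 and 194 − c degrees of freedom. R² is the outcome variance explained by the covariates, and VIF is the inflation from their collinearity with lens. To two decimals, c = 3 and c = 5 give the same power:
- R² = 0, VIF = 1: λ = 12.31, power 0.89.
- R² = 0, VIF = 1.25: λ = 9.85, power 0.80.
- R² = 0.2, VIF = 1: λ = 15.39, power 0.95.

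**The case against.** The strongest reply is that the design already controls a good deal. Vision-affecting comorbidity, complicated cases and "Prior intraocular or corneal surgery" are all excluded, and age, axial length and astigmatism are bounded. All lenses share one refractive target, one surgical approach and one follow-up schedule. This stands as partial control: it narrows the scope for imbalance but does not remove it within the permitted ranges.

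Several stronger readings are tempting, and the documents do not support them:
- **That the comparison is biased.** No baseline data are given. The risk follows from the design, but its presence, size and direction cannot be shown. In the mildest case above the effect is close to nil.
- **That lenses were chosen by patient preference in routine care.** The text says only that patients received them.
- **That no planned analysis could reveal an imbalance.** Descriptive summaries are planned, and the categorical tests might be applied to patient characteristics. The SAP does not promise a baseline table by lens, but the accurate statement is that nothing planned would correct an imbalance.
- **That the GEE excludes covariates.** Its single line lists no model terms at all. It is correct only that none is named.
- **That the plan claims causal lens effects.** It compares outcomes by lens without a caveat about selection, and the causal reading is an inference.

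It is also fair to object that the document is written largely in the past tense and reports post hoc power. An adjusted model introduced now may come after the data were seen, and adjustment cannot reach unmeasured selection. Both points shape the remedy but do not remove the need for one.

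**Conclusion.** The point holds as a gap in the analysis: a non-randomised primary comparison with no stated basis for lens choice, no named covariate, and only partial control through eligibility. Depending on assumptions that the documents cannot settle, the consequence runs from negligible (about 6% rejection at a 0.06 SD bias) to serious (35% to 45% at 0.32 SD). Those rates assume no true lens effect, equal groups, 197 patients and a single confounder acting through the stated r and d. They illustrate what an unadjusted test tolerates and do not estimate what happened in this study. The key covariates were needed to apply the eligibility criteria and should be in the records, so leaving them out of every analysis is avoidable.

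**What to change.** 1. State how the lens was chosen for each patient, and tabulate baseline characteristics by lens with standardised differences.
2. For each binocular acuity and satisfaction outcome, base the comparative conclusion on a linear model with lens group, age, mean axial length and mean corneal astigmatism, using robust standard errors. Add sex and preoperative corrected acuity if they are charted; the documents do not say that they are. Use the same covariates in any eye-level GEE.
3. Add surgery date as a sensitivity analysis only where the lenses' periods of use overlap. Elsewhere the adjustment would be extrapolation.
4. Report the unadjusted tests alongside. If the data have already been seen, label the adjusted analysis post hoc.
5. State that unmeasured selection remains, for example patient expectations that could influence both lens choice and satisfaction.

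The cost is 3 to 5 degrees of freedom, some chart extraction and reanalysis, and possibly some precision if the covariates are collinear with lens. No new patients are needed.

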## Study Period

June 2019 to January 2024. Primary completion in 2024.

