## Inclusion Criteria

- Age-related cataract in both eyes.
- Eligible for bilateral IOL implantation.
- Willingness to complete follow-up.

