## **Ethics**

The study adhered to the Declaration of Helsinki and was approved by the Sakarya University Faculty of Medicine Non-Interventional Ethics Committee (Approval 2022/294). Written informed consent was obtained.

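### Three lenses are compared over a 56-month study period with no concurrency rule and no surgery-date term, so if lens mix and outcomes both shifted over time, the shift would be counted as a lens effect

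*Combined protocol and SAP*

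**What the plan says.** - **Study Design:** "Consecutive, comparative, retrospective case series of patients undergoing bilateral phacoemulsification with implantation of the same IOL model in both eyes". Allocation is not randomised, and no rule says how or when a lens model was chosen.
- **Study Period:** "June 2019 to January 2024. Primary completion in 2024". One pooled period is given. The text does not say whether it covers surgery only or surgery plus follow-up.
- **Interventions / Exposures:** "Patients received one of the following IOLs in both eyes". Three models are listed, with no dates of availability or use.
- **Inclusion Criteria, Exclusion Criteria and Analysis Population:** none of these sets a calendar restriction.
- **Comparative Analyses:** the first method is "Kruskal–Wallis tests with Dunn–Bonferroni post hoc comparisons for non-normally distributed continuous outcomes". The others are one-way ANOVA with Tukey HSD, chi-square or Fisher tests, and one GEE for binocular UIVA whose stated purpose is within-subject correlation. Surgery date does not appear as a covariate, stratum, matching variable or sensitivity analysis.

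**The concern.** In a non-randomised comparison, calendar time confounds the lens effect when two things hold together: the lens mix changes over the period, and the outcomes change over the period for reasons unrelated to the lens. Candidate reasons include biometry, testing practice, the way the questionnaire was given, and patients' expectations. Three of the six primary outcomes are self-rated satisfaction scores, which may be open to such shifts.

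This is distinct from patient characteristics driving lens choice. Groups alike in age, axial length and astigmatism could still come from different years, so adjusting for baseline characteristics would not remove a period effect. The planned unadjusted tests could neither detect nor correct one. At stake are the pairwise lens differences and the type I error rate of the primary comparisons.

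**Working it through.** **Inputs from the documents.** Study period June 2019 to January 2024; n = 197, three groups, alpha 0.05 and f = 0.25 (Sample Size).

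**Inputs assumed, because the documents do not give them.** Groups of 66/66/65; no true lens difference; linear drift totalling D within-group SDs over 56 months; neighbouring lenses' mean surgery dates g months apart.

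**1. Length of the period.** (2024 − 2019) × 12 + (1 − 6) + 1 = 56 calendar months, counted inclusively. If January 2024 is the last 6-month visit, surgery spans about 56 − 6 = 50 months.

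**2. The plan's own power figure.** With λ = N·f² = 197 × 0.0625 = 12.31 on 2 and 194 df, the noncentral F gives power 0.887, not the stated 0.96. That mismatch is a separate matter. Here 0.887 serves only as the baseline for the cost of adjustment.

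**3. False-positive rate when drift is ignored.** The group means are shifted by −gD/56, 0 and +gD/56 SD. Then λ = Σ nᵢ(μᵢ − μ̄)², and the rejection rate is P(F′(2, 194; λ) > 3.042). For example, with D = 0.5 and g = 12 the shift is 12 × 0.5/56 = 0.107 SD, λ ≈ (66 + 65) × 0.107² ≈ 1.50, and the rate is 0.177.

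| Total drift D | Gap g (months) | Spurious outer-lens difference, 2gD/56 (SD) | Omnibus false-positive rate |
|---|---|---|---|
| any | 0 (equal mean dates) | 0 | 0.050 |
| 0.25 | 6 | 0.05 | 0.057 |
| 0.25 | 12 | 0.11 | 0.079 |
| 0.5 | 6 | 0.11 | 0.079 |
| 0.5 | 12 | 0.21 | 0.177 |
| 1.0 | 6 | 0.21 | 0.177 |
| 1.0 | 12 | 0.43 | 0.578 |

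Using 50 months in place of 56 changes little: for D = 0.5 and g = 12 the outer difference becomes 2 × 12 × 0.5/50 = 0.24 SD.

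**4. Check with other patterns of use.** A simulation with 4000 runs per scenario gave, for drifts of 0.25 / 0.5 / 1.0 SD:
- concurrent use: 4–6% at every drift;
- partly overlapping windows: 8% / 17% / 49%;
- use in sequential thirds: 12% / 36% / 93%.

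**5. Effect of a surgery-year factor.** With D of 0.5 or 1.0 and g of 6 or 12, a year factor in the model brought the simulated rate back to 0.043–0.061.

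**6. Cost of that factor.** Losing a few degrees of freedom costs almost nothing, but that is the whole cost only when lens and year are unrelated. Take each lens as used over a 44-month window when g = 6, or a 32-month window when g = 12. The three windows then fill the period, since 44 + 2 × 6 = 56 and 32 + 2 × 12 = 56. With evenly spaced lens means, simulated power at f = 0.25 falls from 0.89 to about 0.81 and about 0.57. A rough variance-inflation guide agrees: 0.78, 0.59 and 0.32 if time explains 25%, 50% and 75% of lens assignment.

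**The case against.** The strongest objection is that the bias is hypothetical. It needs both uneven lens use over time and drifting outcomes, and the documents report neither. The drift sizes and gaps above have no source in the documents. The protocol also describes one surgical technique, one refractive target, fixed test distances and photopic testing for everyone, which narrows the room for drift without excluding it. All of this stands, and it is why the point is conditional.

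It is also fair to say that requiring year adjustment in every primary comparison, before anyone knows whether lens use differed by year, could give up much precision for nothing. That stands too. Unadjusted lens selection by patient or surgeon may well be the larger weakness, and a year term would not cure it.

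Three stronger readings are tempting but unsupported:

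- **That the lenses were in fact used in different years.** The average of 197/56/3 ≈ 1.2 patients per lens per month says nothing about clustering in time. Equally, describing the series as consecutive concerns how cases were captured and does not establish concurrent use.
- **That the ethics approval splits the cohort into two differently recruited parts.** The Ethics section gives only "Approval 2022/294". The year is read from the number and no date is stated. A period that straddles an approval creates no bias by itself.
- **That the criterion "Willingness to complete follow-up" shows a change in how patients entered.** Completion of the 6-month visit is required of everyone, whatever the date, under Exclusion Criteria and Analysis Population. Rewording the criterion would not address drift.

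**Conclusion.** The point holds as a conditional risk that the plan leaves unexamined. It is not a demonstrated bias. As written, the analysis cannot separate a period effect from a lens effect, and a reader has no lens-by-date information with which to rule one out.

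Under the assumed 6- to 12-month gaps, the consequence runs from negligible (about 6–8% false positives at 0.25 SD of drift) to serious (18–58% at 1 SD), and there is none if use was concurrent. These rates rest on linear drift, near-equal groups and no true lens effect. The label is a cheap improvement: a table and two sensitivity analyses, with no change to the primary tests.

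**What to change.** Under Comparative Analyses:

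1. Tabulate patients per lens per surgery year, with the first and last implantation date for each model.
2. Add as pre-specified sensitivity analyses of the primary binocular outcomes: (a) the lens comparison with a surgery-year factor in the ANOVA or linear model, or a rank test stratified by year (van Elteren type); and (b) the planned comparison restricted to the dates when all three lenses were in use. If results have already been seen, label both as post hoc.
3. State that a lens pair with little overlap in time cannot be separated from period.
4. Say in Study Period whether the dates cover surgery only or surgery plus follow-up.

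The cost is SAP wording and a little programming, provided surgery date is in the records. That is likely, but the documents do not say so. The adjusted intervals will be wider where lens and year are related, as the power figures above show, and the common-window analysis will have fewer patients. Where overlap is poor, the wider interval is the honest answer. Keeping these as sensitivity analyses avoids imposing that loss on the primary comparison if use proves concurrent.

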## Study Population

Adults aged 45–75 years with age-related cataract undergoing bilateral cataract surgery.

## Inclusion Criteria

- Age-related cataract in both eyes.
- Eligible for bilateral IOL implantation.
- Willingness to complete follow-up.

## Exclusion Criteria

- Preoperative corneal astigmatism  $\geq 1.0$  D.
- Axial length  $\leq 21$  mm or  $\geq 26$  mm.
- Prior intraocular or corneal surgery.
- Ocular comorbidities affecting vision (severe dry eye, amblyopia, ocular surface disease, corneal pathology, retinal diseases, uveitis, glaucoma, pseudoexfoliation, pterygium).
- Intraoperative or postoperative complications, or failure to complete 6-month follow-up.

## Interventions / Exposures

Patients received one of the following IOLs in both eyes:

- Monofocal: Tecnis ZCB00 (Johnson & Johnson Vision)
- Enhanced monofocal: Tecnis Eyhance ICB00 (Johnson & Johnson Vision)
- EDOF: Asqelio EDOF ETLIO130C (AST Products)

## Surgical Technique and Postoperative Care

Standard phacoemulsification using manufacturer-recommended injector systems. IOL power selected to target approximately -0.25 D (first myopic-leaning power). Postoperative regimen: topical 0.5% moxifloxacin + 0.1% dexamethasone five times daily for one week, tapered over three weeks. Follow-up at 1 day, 1 week, 1 month, 3 months, and 6 months.

## Assessments and Outcome Measures

At 6 months, visual acuity measured at distance (6 m), intermediate (66 cm), and near (40 cm) under photopic conditions, converted to logMAR. Refraction (manifest and objective), binocular defocus curves (+1.00 D to -2.50 D in 0.50 D steps), and patient questionnaires on halos/glare and spectacle independence were recorded.

### Primary Outcomes (6 months):

- Binocular UDVA, UIVA, UNVA (logMAR).
- Patient satisfaction scores for distance, intermediate, and near spectacle-free vision (0–10 scale).

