## **Sample Size**

A post hoc power analysis (one-way ANOVA; Cohen's  $f = 0.25$ , alpha 0.05, three groups,  $n = 197$ ) yielded power of 0.96.

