## **Significance Threshold**

Two-tailed  $p \leq 0.05$  considered statistically significant.

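### Six primary outcomes are each tested at 0.05 with no error control across them; if no lens differs on any, the chance of at least one false overall test is 26.5% under independence and lower under correlation.

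*Combined protocol and SAP*

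**What the plan says.** The protocol's list of primary outcomes at 6 months has two entries covering six variables: "Binocular UDVA, UIVA, UNVA (logMAR" and "Patient satisfaction scores for distance, intermediate, and near spectacle-free vision (0–10 scale". The Objectives section puts acuity at all three distances and "patient satisfaction at 6 months among monofocal, enhanced monofocal, and EDOF IOLs" into one primary objective. It names no lead outcome, no order of testing, and no rule that all six must succeed.

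The SAP's Significance Threshold section sets a single two-tailed p ≤ 0.05 as "considered statistically significant", without distinguishing primary from secondary outcomes.

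The SAP's Comparative Analyses section lists these methods for continuous outcomes:

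- "Kruskal–Wallis tests with Dunn–Bonferroni post hoc comparisons for non-normally distributed continuous outcomes"
- "One-way ANOVA with Tukey HSD for key binocular outcomes when appropriate"
- "GEE model with exchangeable correlation structure for binocular UIVA to account for within-subject correlation"

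The protocol's Sample Size section describes one one-way ANOVA (f = 0.25, alpha 0.05, three groups, n = 197), which "yielded power of 0.96".

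**The concern.** The plan does correct for multiple comparisons, but at one level only. Dunn–Bonferroni and Tukey HSD protect the three lens pairs once a single outcome has been tested. The GEE deals with correlation within a patient. None of these limits the chance that at least one of six overall tests is significant when the lenses do not differ.

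Since the plan does not say what result would answer the primary objective, a significant difference on any one outcome meets the only criterion it sets. The 5% threshold then holds for each outcome separately but not for the primary objective as a whole. The power statement has the same limit: it describes one test, not six.

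**Working it through.** **Inputs from the documents.** Six primary outcomes (three acuities, three satisfaction scores); three lens groups; alpha 0.05 two-tailed for each test; n = 197; f = 0.25; stated power 0.96.

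**Assumptions.** n = 197 is the total number of patients, split 66/66/65. Outcomes share a common correlation, which the documents do not give, so a range is shown. One overall test is counted per outcome.

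**1. The plan's own figure.** Power is the probability that a noncentral F variable with df (2, 194) and noncentrality N × f² exceeds the central F critical value.

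- Noncentrality: 197 × 0.25² = 12.31.
- Power at alpha 0.05: 0.887, not the stated 0.96.
- Alternative readings: 197 per group gives more than 0.999, and 394 eyes gives 0.996. Neither matches.
- Power of 0.96 would need N = 264, or f of about 0.29 at n = 197.

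The baseline used below is therefore 0.887. This discrepancy does not affect the error-rate results.

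**2. All six outcomes null.** If independent, the chance of at least one false significant overall test is 1 − 0.95⁶ = 1 − 0.7351 = 0.265.

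For correlated outcomes, six three-group ANOVAs were simulated with no true difference (20,000 runs, Monte Carlo error about 0.3 percentage points):

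| Assumed common correlation | At least one of six significant |
|---|---|
| 0 (exact) | 26.5% |
| 0.3 | 24.8% |
| 0.5 | 21.7% |
| 0.7 | 17.1% |
| 0.8 | 14.6% |
| 0.9 | 11.3% |

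Kruskal–Wallis gives much the same: 26.6% at 0, 21.4% at 0.5 and 14.5% at 0.8. The choice between the two tests does not matter here.

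**3. Only some outcomes null.** Only truly null outcomes can produce a false overall result.

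- Three null, independent: 1 − 0.95³ = 14.3%.
- Two null, independent: 1 − 0.95² = 9.75%. By simulation, about 8% to 9% at correlations 0.5 to 0.7, and about 7% at 0.9.

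**4. With control across six.** The strictest Holm step is 0.05/6 = 0.0083. Power for f = 0.25 and n = 197 at that level is 0.70, against 0.887 at 0.05. Later Holm steps are less strict (0.05/5 = 0.01, then 0.0125, and so on up to 0.05).

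**5. Lens pairs after the overall tests.** Suppose one lens truly differs from the other two on all six outcomes, and those two do not differ from each other. All six overall tests can then be correctly significant, leaving one null pair per outcome. Tukey at 0.05 gives about 1.9% per null pair, so 1 − (1 − 0.019)⁶ is about 11% across six independent outcomes. Bonferroni over three pairs gives 0.05/3 = 1.67% per pair, so about 10%. Holm on the overall tests alone therefore does not control pairwise claims across outcomes.

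**The case against.** **The percentages are conditional.** The 26.5% and its correlated counterparts require that no lens differs on any of the six outcomes. The protocol's Background describes lenses designed to extend intermediate and near vision, so the sponsor plainly does not expect that. A reader might infer that the trial carries an unconditional risk somewhere between 16% and 26%. The documents do not support this: they neither say which outcomes are null nor give a correlation, and a floor near 16% comes only from choosing a correlation of about 0.7 to 0.75. This part of the objection stands, and the size must be given with its conditions.

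**The study is descriptive.** It is a retrospective case series whose objective is to compare, and no success rule or superiority claim is written down. A reader might infer that the sponsor intends to declare success on any single outcome; the documents do not say so. How strictly to adjust across clinically distinct distances is partly a matter of judgement. However, the plan does not call itself exploratory. It designates primary outcomes and sets a significance threshold for them, and so should say how six results are to be read together.

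**Multiplicity is already handled.** This does not stand. Both post hoc procedures work within an outcome, and the GEE does not address multiplicity.

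**Holm on six p-values is not a complete remedy.** This stands in two respects. Binocular UIVA can be tested by Kruskal–Wallis, ANOVA or GEE, so its p-value is not uniquely defined. And control of the overall tests does not extend to lens-pair claims, as step 5 of the working shows.

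**Conclusion.** The gap is certain: nothing in the protocol or SAP controls error across the six primary outcomes. Its size is less certain. With all six null, the chance of at least one false overall test runs from 26.5% under independence to about 11% at an assumed correlation of 0.9, still more than twice the nominal 5%. With only two null it is about 7% to 10%. These figures count one overall test per outcome, so they omit any further chance of a false result from choosing among three methods for binocular UIVA.

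It would overstate the point to say that the plan has no multiplicity control at all, or that any particular finding is false. The supportable conclusion is narrower: the 0.05 threshold does not hold for the primary objective taken as a whole. The sponsor should correct this; the remedy needs no new data.

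**What to change.** 1. Name one overall p-value for each of the six primary outcomes. State for each whether Kruskal–Wallis or ANOVA applies, and for binocular UIVA which of Kruskal–Wallis, ANOVA or GEE governs. Any other analysis of that outcome is supportive.
2. Apply Holm's procedure to the six p-values at an overall 0.05. It is valid under any correlation between outcomes. It also needs no ranking, which is an advantage when the data may already be known.
3. Interpret lens-pair comparisons only for outcomes that pass. Then either state that pairwise error is controlled only within each outcome, or apply Holm to the full set of 6 × 3 = 18 unadjusted pairwise p-values.
4. Report the secondary outcomes (monocular and corrected acuities, refraction, defocus curve, halo and glare) as exploratory, with unadjusted 95% confidence intervals.
5. Correct or explain the power of 0.96, so that the cost of adjustment is judged against a reproducible baseline.

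**Cost.** The SAP text changes, and because the SAP describes its analyses in the past tense, the primary results probably need to be re-read against the Holm thresholds and re-reported. Power for f = 0.25 at n = 197 falls from 0.887 to 0.70 at the strictest step, less at later steps. The 18-comparison option is stricter again for pairwise claims, starting at 0.05/18 = 0.0028.
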